N=150). In the same pilot trial, 77% of subjects completed the 8 week trial; we anticipate similar retention in the proposed study. Thus, a randomized sample size of 100 participants per treatment arm (total N=200) would maintain power to detect the clinically significant difference stated above in the presence of ~25% attrition during the study. Similarly, in the same pilot study, reductions in craving were significantly greater in the NAC vs. placebo treated group ($\Delta=3.0$ vs. $\Delta=1.3$). The randomized sample size of 100 per treatment arm provides >95% power with a type 1 error rate of 5% to detect this effect in the presence of 25% attrition during the study period. It is hypothesized that NAC reduces the risk of drinking as compared to placebo. With this stated sample size, a 25% decreased risk in the consumption of standard drinks can be detected with at least 80% power between the NAC and placebo treated arms (Risk Ratio=0.75).

Power calculations for the neuroimaging component are based on previous studies of individuals with PTSD or substance use disorders. Based on our previous work and the extant literature, we conservatively estimate ~70% of participants (140/200) will be eligible and volunteer for the neuroimaging component. A recent study of 29 individuals (PTSD=14, controls=15) observed significant differences in PFC-AMY resting state connectivity⁵⁰. The effect size for this difference was 0.8 (Cohen's d). Thus, power (1- β) reaches .80 with a total sample size of N=26 (two-tailed, alpha=.05). Another study of 45 cocaine-dependent individuals found that individuals who relapsed (n=24) had significantly lower PFC-AMY connectivity at baseline as compared to individuals who did not relapse (n=21)⁴⁹. The effect size for this reduction was 1.0. Thus, power (1- β) reaches .80 with N=34 subjects (two-tailed, alpha=.05). For exploratory hypothesis 4, the only published study of NAC effects on brain glutamate found that one dose of NAC vs. placebo administered 1 hour prior to scanning, led to a significant modification in ACC glutamate with an effect size of $d = 2.6$ in individuals with cocaine dependence. Although the present study will be examining the effects of chronic NAC treatment in individuals with AUD and PTSD, an effect of similar magnitude would provide power > 0.99. The present study is therefore well-powered to test the proposed hypotheses.

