Hypotheses. The hypotheses and statistical approaches for testing each hypothesis are listed below.

Hypothesis 1: NAC treatment will result in significantly greater reduction in AUD severity and craving, as compared to placebo. To test this hypothesis, a mixed effects modeling framework will be specified with the total number of standard drinks consumed and the OCDS total score as the primary outcomes. A Poisson distribution will be assumed with a logarithm link function to assess the effects of NAC treatment and the baseline number of total standard drinks (past 60 days) prior to treatment entry. Over-dispersion due to a wider than expected distribution in discrete count models (from heterogeneity) can have a significant impact on parameter inference, thus when detected, a negative binomial (NB) distribution will be specified. Further, data collected in substance abuse studies often contain a preponderance of zeros, and these zeros in the distribution can be considered sampling zeros in the Poisson process¹²⁵. If this excess is present in the distribution, two-part Hurdle models (Poisson and NB) will be explored¹²⁶⁻¹²⁷. The hurdle part of the model will allow us to estimate the probability of abstinence during the study period (as an odds ratio) while the Poisson/NB portion will allow for the assessment of the risk of an increase in using days beyond zero during the study period (as a risk ratio). Model fit of the Poisson (Hurdle Poisson) model will be compared to the Negative Binomial (Hurdle NB) model by practical examination of the deviance and Pearson chi-square values (Likelihood Ratio) with respect to their degrees of freedom. Baseline alcohol use and craving will be included in pertinent models as covariates. Additional alcohol use outcomes will be assessed: percentage of drinking days (DD) and the number of heavy drinking day (HDD). End of study abstinence will be assessed using logistic regression models. DD and HDD will be assessed using count models.

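### If zeros are in excess, does the plan leave open which effect on total drinks decides Hypothesis 1?

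*Combined protocol and SAP*

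**What the plan says.** Hypothesis 1 (Statistical Analyses, Hypotheses) sets up a mixed model with "the total number of standard drinks consumed and the OCDS total score as the primary outcomes". For drinks the starting point is a Poisson model with log link. If over-dispersion is detected, the plan commits to an NB distribution instead.

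For zeros it notes that "data collected in substance abuse studies often contain a preponderance of zeros" and continues that, if the excess is present, "two-part Hurdle models (Poisson and NB) will be explored". It then explains the two parts: the hurdle gives an odds ratio for abstinence, "while the Poisson/NB portion will allow for the assessment of the risk of an increase in using days beyond zero during the study period", the latter as a risk ratio.

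The fit check reads "Model fit of the Poisson (Hurdle Poisson) model will be compared to the Negative Binomial (Hurdle NB) model". It compares Poisson with NB inside each family, not hurdle with non-hurdle.

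Drinking days, heavy drinking days and a logistic model for end-of-study abstinence follow as additional alcohol outcomes.

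Power and Sample Size gives one effect for drinks, a 25% lower risk in standard drinks consumed, "between the NAC and placebo treated arms (Risk Ratio=0.75").

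**The concern.** The plan expects zeros to be common, so the hurdle branch may well be reached. Once there, three effects are available: the overall ratio of mean drinks, the ratio among those who drank, and the odds ratio for abstinence. They answer different questions. The ratio among drinkers also conditions on something that happens after randomisation.

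The text gives no threshold for excess, no rule for choosing hurdle over non-hurdle, and no statement of which effect would carry the drinks outcome. The count part is worded in days although the outcome is drinks, and it is the only effect in that paragraph called a risk ratio, the same label used in the power statement.

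If this were truly open, the deciding effect could be picked after seeing results by arm. Letting either hurdle part succeed at 5% would raise the type I error to 1 − 0.95² = 9.75% (10.1% when simulated).

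**Working it through.** **1. The plan's own figure.** At least 80% power for a ratio of 0.75 can be neither reproduced nor refuted, because no mean count or dispersion is given. The number per arm follows from the CAPS calculation, 75/(1 − 0.25) = 100, "in the presence of ~25% attrition during the study". Carrying 75 evaluable per arm over to drinks is an assumption.

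For an overall log ratio, Var = (1/μ + 1/(0.75μ) + 2k)/n, where μ is the placebo mean and k the NB dispersion. At two-sided 5% and 80% power the bracket may be at most n(ln 0.75)²/(1.960 + 0.842)²:

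- 75 per arm: 0.791, so k ≤ 0.791/2 ≈ 0.40 with a large mean.
- 100 per arm: 1.054, so k ≤ 0.53.

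The power statement can therefore be met by an overall ratio and needs no two-part test.

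**2. How far the effects can separate.** For raw means of one total per person, ratio among drinkers = overall ratio × (1 − p placebo)/(1 − p NAC), where p is the proportion abstinent. Take an overall ratio of 0.75 and assume 20% abstinent on placebo:

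| Abstinent on NAC | Ratio among drinkers |
|---|---|
| 20% | 0.75 × 0.80/0.80 = 0.75 |
| 30% | 0.75 × 0.80/0.70 = 0.86 |
| 40% | 0.75 × 0.80/0.60 = 1.00 |

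The identity is not exact for a zero-truncated coefficient or for weekly records.

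**3. Simulation.** All inputs are assumed: 75 per arm, mean 40 and CV 1 among drinkers, baseline correlation 0.5, 20% abstinent on placebo, overall ratio 0.75. The first four rows use log-link (or logistic) models adjusted for baseline drinks, with robust errors for the ratios, over 4,000 runs. The NB rows use model-based errors and only 300 runs. Entries are the percentage of trials with significant benefit, or with the two ratios disagreeing on significance.

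| Abstinent on NAC | 20% | 30% | 40% |
|---|---|---|---|
| Overall ratio | 36 | 34 | 31 |
| Ratio among drinkers | 44 | 18 | 4 |
| Abstinence odds ratio | 3 | 29 | 78 |
| The two ratios disagree | 16 | 19 | 27 |
| NB: overall ratio | 28 | 19 | 13 |
| NB: ratio among drinkers | 59 | 26 | 5 |
| NB: the two ratios disagree | 32 | 14 | 10 |

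The disagreement rates do not measure the cost of the gap. At 20% abstinent in both arms each true ratio is 0.75, yet the tests disagree in 16% of trials (32% under NB). That is sampling noise and unequal power, not two different questions. Under NB, which the plan specifies for over-dispersed data such as these, disagreement falls as the abstinence effect grows, the reverse of the robust result.

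**4. The passages side by side.**

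- Over-dispersion brings a commitment to change the distribution. Excess zeros bring only exploration. The contrast stands within one paragraph.
- The named outcome is total drinks, and the one powered effect is a ratio for drinks consumed.
- The fit check never sets hurdle against non-hurdle. A replacement would need that comparison; a supplement does not.
- The General paragraph puts all analyses on all randomised subjects. The overall ratio meets this directly; a ratio confined to post-randomisation drinkers does not.

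All four point to the Poisson/NB ratio as the test of drinks.

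**The case for a change.** The best case for a change is that none of this is stated. The hurdle text sits inside the test of the primary outcome, ahead of the additional outcomes, and shares its fit check. The separate logistic model concerns abstinence at the end of the study, whereas the hurdle part covers the study period, so its placement does not settle the hurdle's role. The ranking of power reverses with mechanism, which makes a late choice open to challenge. One sentence would close the matter.

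The literal omission stands, and so does the missing threshold for excess zeros. The rest carries less weight:

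- A log-link count model yields a ratio whichever form is used. The shared label does not tie the powered 0.75 to the count part, and that 0.75 is stated for drinks, not days.
- The wording in days changes no analysis, because the modelled outcome is named as drinks. It may echo the count models planned for drinking days and heavy drinking days.
- No alternative decider is better throughout. The abstinence odds ratio has 78% power if NAC acts only through abstinence but 3% if it acts only on amount drunk. A joint 2-df test of both hurdle parts has no direction: with equal mean drinks in the two arms and 20% against 40% abstinent, it rejected in 84% of simulated trials.
- Hypothesis 1 also has the OCDS score as a primary outcome, so a sentence about drinks would not by itself settle the hypothesis.

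**Conclusion.** No change follows. This is a gap that analysts fill sensibly, plus a slip between days and drinks. On the natural reading, the Poisson/NB ratio in all randomised participants is the test of total drinks and both hurdle parts are supportive. That analysis is valid and matches the single ratio of 0.75 in the power section. No sample size, error rate or stated power in the plan moves.

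Keeping the overall ratio is a fair trade-off. In the simulations it has less power than the abstinence odds ratio if NAC works through quitting, and less than the ratio among drinkers if NAC works on amount, but it does not collapse in either case as those two do (31% to 36% with robust errors; 13% to 28% under NB). These percentages rest on assumed means, dispersion and abstinence rates, and on one total per person instead of weekly records. They illustrate and do not predict.

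The conclusion assumes that the text is followed as it reads. Presenting the ratio among drinkers as the primary result would depart from the written plan, and a reader could see that from the protocol.

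### If the hurdle model is used, its risk ratio is conditional on drinking and need not equal the ratio of total standard drinks in all randomised participants

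*Combined protocol and SAP*

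**What the plan says.** All references are to the Statistical Analyses section of the combined protocol and SAP.

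- **Hypothesis 1, outcome and default model.** The plan names "the total number of standard drinks consumed and the OCDS total score as the primary outcomes". Drinks are modelled as Poisson counts with a log link, or as negative binomial (NB) if over-dispersed. Baseline alcohol use and craving are covariates.
- **Hypothesis 1, excess zeros.** Hurdle models are to be explored if there are too many zeros. The zero part gives an odds ratio for abstinence. For the other part, "the Poisson/NB portion will allow for the assessment of the risk of an increase in using days beyond zero during the study period", expressed as a risk ratio. The unit here is days of use, although the outcome is drinks.
- **Power and Sample Size.** The plan says that "a 25% decreased risk in the consumption of standard drinks can be detected with at least 80% power between the NAC and placebo treated arms", with a risk ratio of 0.75. The sentence before it reads "It is hypothesized that NAC reduces the risk of drinking as compared to placebo". Neither an abstinence rate nor a two-part model is mentioned.
- **General.** Every analysis is to use the full randomised sample.

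The plan has no step that combines the two hurdle parts into an effect on total drinks. It does not say which part, or what joint test, would answer Hypothesis 1.

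**The concern.** In a hurdle model the count part is fitted to non-zero counts only. Whether a participant is above zero is decided after randomisation, and NAC is expected to influence it. Two consequences follow, and they should be kept apart.

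1. **A different quantity.** If NAC changes the proportion abstinent, the ratio among drinkers and the ratio in everyone randomised differ by definition. No bias is needed for this.
2. **Possible selection.** If those who become abstinent on NAC are, say, the lighter drinkers, the remaining NAC drinkers are heavier than their placebo counterparts. The count-part ratio is then not a like-for-like comparison. Baseline drinks and craving may remove only part of this, because they do not fully determine who would drink during treatment.

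At stake is whether the reported risk ratio answers the question the trial was sized for. A reduction in total drinking that comes largely through abstinence could appear beside a count-part ratio close to 1.

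**Working it through.** **Inputs from the documents.** Risk ratio 0.75 with at least 80% power; 100 randomised per arm; about 25% attrition; 5% type 1 error, stated for the CAPS and craving calculations but not repeated for drinks.

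**Assumed.** Two-sided testing for drinks, mean counts, dispersion and abstinence rates. The documents give none of these.

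**Step 1: the plan's own figure.** Attrition agrees: 75/(1 − 0.25) = 100. For NB counts with placebo mean μ and dispersion k,

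Var(log RR) = [(1/μ + k) + (1/(0.75μ) + k)]/n.

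For 80% power at n = 75, this variance must not exceed (ln 0.75)²/(1.960 + 0.842)² = 0.0828/7.849. The largest admissible dispersion is therefore

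k = (75 × 0.0828/7.849 − 2.333/μ)/2 = (0.791 − 2.333/μ)/2,

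which is 0.337 at μ = 20, 0.372 at μ = 50 and 0.390 at μ = 200. The stated power is attainable, but it can be neither confirmed nor refuted without a mean and a dispersion.

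The other possible reading of 0.75 is a ratio of the proportions who drink at all. On that reading, 100 per arm gives 80.2% power at an assumed placebo proportion of 75%. On neither reading is 0.75 a ratio among drinkers.

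**Step 2: how the two ratios relate.** Let a be the proportion abstinent and m the mean drinks among those who drink. The overall mean is (1 − a) × m, so

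overall ratio = [(1 − a_NAC)/(1 − a_placebo)] × (m_NAC/m_placebo).

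**Step 3: ratio among drinkers when the true overall ratio is 0.75.** At placebo abstinence of 20%:

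- NAC 20%: 0.75/(0.80/0.80) = 0.75
- NAC 30%: 0.75/(0.70/0.80) = 0.75/0.875 = 0.857
- NAC 40%: 0.75/(0.60/0.80) = 0.75/0.75 = 1.00

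Over a wider assumed range:

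| Placebo abstinence | NAC equal | NAC +10 points | NAC +20 points |
|---|---|---|---|
| 10% | 0.75 | 0.844 | 0.964 |
| 20% | 0.75 | 0.857 | 1.00 |
| 30% | 0.75 | 0.875 | 1.05 |

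**Step 4: the reverse reading.** If the ratio among drinkers is 0.75 and placebo abstinence is 20%, the overall ratio is 0.75 × 1 = 0.75, 0.75 × 0.875 = 0.656 or 0.75 × 0.75 = 0.562 at NAC abstinence of 20%, 30% or 40%. The count part can therefore understate the effect on total drinks even when it shows a benefit.

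**Limits of the identity.** It is exact for means among drinkers. The coefficient of a zero-truncated model is the ratio of the untruncated means, which is close to this when drinkers' counts are well above zero. Steps 3 and 4 show the change of quantity only. They put no size on selection, which would need the joint distribution of severity and abstinence.

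**The case against.** The case on the other side is substantial.

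- **The branch is contingent.** The default Poisson or NB model already targets the ratio of total drinks. This stands. However, Hypothesis 1 itself notes that an abundance of zeros is common in this field, so the branch is foreseeable.
- **Abstainers are not dropped.** The hurdle model as a whole uses everyone and reports an abstinence odds ratio. End-of-study abstinence, drinking days and heavy drinking days are also analysed. In the 20% versus 40% case the odds ratio is (0.40/0.60)/(0.20/0.80) = 2.67, so the benefit would be visible there. This stands, but an odds ratio and a conditional risk ratio left side by side still give no effect on total drinks.
- **Baseline adjustment and stratification.** Adjustment for baseline use and craving, with randomisation stratified by AUD severity, should reduce selection. Neither changes the fact that the ratio is conditional.
- **The unit is not settled.** With weekly TLFB data in a mixed model, conditioning could be on drinking periods rather than on participants. Those periods are also defined after randomisation.

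A reader might infer that the count-part ratio is biased in any case, that NAC would be reported as harmful among drinkers, or that the hurdle model costs a known amount of power. The documents support none of these. With equal abstinence the two ratios agree, and the plan nowhere says that the count part decides Hypothesis 1 or is to be compared with 0.75. Any false-harm or power figure would rest on drink distributions the documents do not give. As Step 1 shows, dispersion alone could account for low power.

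**Conclusion.** The concern holds in conditional form. If excess zeros lead to the hurdle model and NAC affects abstinence, the count-part risk ratio is not the all-randomised ratio of the plan's own primary outcome. It may also be distorted by selection if the remaining drinkers differ in severity between arms.

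For a true overall ratio of 0.75, the corresponding ratio among drinkers runs from 0.75 to 1.05 over assumed placebo abstinence of 10% to 30% with NAC 0 to 20 points higher. These abstinence rates are illustrative. Taking 0.75 as a ratio of total drinks is the natural reading of Power and Sample Size, but not the only one, since that paragraph also speaks of the risk of drinking. The mismatch between days of use and standard drinks in Hypothesis 1 needs correcting whichever reading is taken.

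**What to change.** State that the treatment effect on drinking for Hypothesis 1 is the ratio of overall mean standard drinks in all randomised participants, whether or not zeros are in excess. Name one of two estimators in advance:

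1. **The baseline-adjusted NB mean model already planned, with robust standard errors.** This is the simpler choice. Excess zeros alter the variance but not the definition of the mean ratio.
2. **If a hurdle model is used, a recombined estimate.** For each participant, under each arm, multiply the predicted probability of any drinking by the predicted mean if drinking (the zero-truncated mean). Average over the baseline covariates of everyone randomised and take the ratio, with a bootstrap or delta-method interval.

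Report the abstinence odds ratio and the count-part ratio as descriptive components. Replace days of use with standard drinks in the description of the count part, and state whether a zero refers to a participant or to a period.

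The cost is SAP wording and, for the second option, a short extra analysis step and possibly a wider interval. No new data or participants are needed.

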For hypotheses 3A and 3B, the following preprocessing and analytical parameters will be used. Preprocessing: Post-acquisition preprocessing and statistical analysis of imaging data will be performed using FEAT (FMRI Expert Analysis Tool) Version 5.98, part of FSL (FMRIB's Software Library). Data will be preprocessed using scripting tools from FEAT. Non-brain signal will be removed using FSL's BET brain extraction. Scans will be corrected for motion using FSL's linear registration and scans will be spatially smoothed using a Gaussian kernel of 8 mm FWHM. Participants with head motion ≥ 0.2 mm will be excluded from the analyses¹²⁷. Motion artifacts will be identified and scrubbed from each subject's data. Scans will be spatially co-registered with a standardized anatomical template (Montreal Neurological Institute) using a 12 parameter affine transformation. Analysis: Functional connectivity will be measured using a psychophysiologic interaction seed-based approach¹²⁹⁻¹³⁰. PPI analysis is used to assess the functional coupling between different brain regions. The PPI is defined as the change in connectivity of one area (i.e., the seed region) to another in relation to the experimental context (e.g., alcohol vs. neutral cues). PPI analyses for resting state, trauma and alcohol cues will be performed separately. Customized sq. wave forms representing the trauma run (1=trauma block and -1=neutral block) and the alcohol cue run (1=alcohol block and -1=neutral block) the duration of each block will be convolved with a double-gamma hemodynamic response function. A mask of the seed region will be made using a 12-mm diameter sphere located in the center of the AMY using the MNI coordinates (x, y, z = ± 22 , 0, -22). The transformation parameters described above will also be applied to the mask. For each subject, the mean corrected and high pass filtered time series of the BOLD signal in the AMY will be extracted and used in a single subject whole brain PPI analysis. The PPI model will include the task vector, time series of the BOLD signal in the AMY, a term representing the positive task x seed interaction, and a term representing the negative task x seed interaction. The first level analysis will generate contrast images of the parameter estimates for each of the four regressors. Voxels will be thresholded at $Z > 2.3$ using a corrected cluster threshold of $p = 0.05$. The contrast images of the parameter estimates of the positive and negative task x seed interactions will be combined for group-level t-tests to identify regions that exhibited altered connectivity with the AMY during the trauma and alcohol cues as compared to neutral cues. All group-level results will be thresholded at $Z > 2.3$ using a corrected cluster threshold of $p = 0.05$. Separate linear regression tests will be used to test for associations between PFC-AMY connectivity at baseline and improvement in AUD and PTSD symptoms during treatment. Changes in total standard drinks will be regressed against the parameter estimate obtained from the center voxel from each cluster that exhibited a significant task x seed interaction with the AMY at rest and in response to the alcohol cues (Hypothesis 3A). Changes in CAPS-5 total scores will be regressed against the parameter estimate obtained from the center voxel from each cluster that exhibited a significant task x seed interaction with the AMY at rest and in response to the trauma cue (Hypothesis 3B). Further exploratory analyses will examine change in PFC-AMY connectivity from pre- to post-treatment and associations with alcohol and PTSD outcomes, both within and between medication groups.

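### The first-level connectivity model enters a positive and a negative task-by-seed term together, so their separate estimates are not identifiable or are imprecise, and the plan does not say how to combine them.

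*Combined protocol and SAP*

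**What the plan says.** All of this is in the Statistical Analyses section, in the analysis paragraph for Hypotheses 3A and 3B, unless noted.

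- The target is one quantity: "The PPI is defined as the change in connectivity of one area (i.e., the seed region) to another in relation to the experimental context".
- Each cue run has one signed task vector: "the alcohol cue run (1=alcohol block and -1=neutral block" for alcohol and "1=trauma block and -1=neutral block" for trauma.
- The first-level model holds the task vector, the amygdala time series, "a term representing the positive task x seed interaction, and a term representing the negative task x seed interaction".
- Four estimates are promised: "The first level analysis will generate contrast images of the parameter estimates for each of the four regressors".
- At group level, "The contrast images of the parameter estimates of the positive and negative task x seed interactions will be combined for group-level t-tests". The stated aim is to find regions whose coupling with the amygdala differs between cue and neutral. No weights or signs are given.
- For 3A and 3B, change in drinks or in CAPS-5 is then regressed on a parameter estimate taken at the middle voxel of each significant cluster. The text does not say which of the two interaction estimates this is.

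The Neuroimaging Component section describes each cue run as six minutes split into a three-minute cue block and a three-minute neutral block, with no rest block, and a TR of 2000 ms.

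**The concern.** One signed task vector and one seed define one interaction. A model with two interaction terms plus the seed asks for more separate quantities than two contexts can supply: two contexts give two seed slopes, while the seed, positive and negative terms give three slope coefficients.

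If the separate coefficients are not unique, their images depend on how the software resolves the redundancy. The interaction image matters because it selects the clusters and then supplies the predictor in the cue-based regressions of Specific Aim 3. An analyst who follows the text could carry forward the right effect, half of it, zero or mostly noise.

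**Working it through.** **Inputs.** From the plan: 360 s / 2 s = 180 volumes per run; two blocks of 90 volumes coded +1 and -1; convolution with a double-gamma response. Assumed, because the plan gives no values: standard double-gamma shape parameters and an autoregressive seed series. A true interaction of 0.5 per unit of task coding was simulated, which is a cue-minus-neutral slope difference of 0.5 - (-0.5) = 1.0.

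**Model.** With task T, seed S, positive term P and negative term N,

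y = b0 + b1·T + b2·S + b3·P + b4·N + error.

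The plan does not define N, so four readings were checked. The plan's own figure is four separately estimated regressors. Ranks below exclude the intercept; add one to include it.

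**Reading 1: N = -P (mirror image).** The last two terms collapse to (b3 - b4)·P. Rank is 3 of 4. Neither b3, nor b4, nor b3 + b4 is estimable; b3 - b4 is. A pseudo-inverse fit gives b3 = 0.25 and b4 = -0.25. The sum is 0.25 + (-0.25) = 0 in every run. The difference is 0.25 - (-0.25) = 0.50. Simulated over 1,000 runs, the difference averaged 0.4999 (SD 0.0720). The ordinary three-regressor model gave the same value and SD, and the two fits never differed by more than 5e-15.

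**Reading 2: P = seed in the cue block, N = seed in the neutral block, unconvolved.** The two blocks fill the run, so P + N = S. Rank is again 3 of 4. The seed, positive and negative coefficients are not separately estimable; b3 - b4 is (mean 0.97, SD 0.14).

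**Reading 3: as Reading 2, with convolved blocks.** Rank is 4, because the response lag stops P + N from equalling S exactly. The median variance inflation factor (VIF) per term was between about 53 and about 580 across the seed and response assumptions tried. The difference is stable (mean 1.01, SD 0.13 against a true 1.0); the sum is not (SD 1.96).

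**Reading 4: P and N = seed times the positive and negative parts of the convolved task vector.** Rank is 4, with a VIF of about 27 to 54 per term. Here N carries its own minus sign, so the interaction is the sum, b3 + b4 (mean 1.00, SD 0.15). The difference is unstable (SD 1.19).

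**Single signed term.** The VIF is 1.01 to 1.05.

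**What the VIFs mean.** The standard error of a separate term grows by √VIF: √30 ≈ 5.5 and √580 ≈ 24. That applies to the separate terms only. On Reading 3, the standard error of the cue-minus-neutral contrast relative to the single-term model had a median ratio of 1.00 and a maximum of 1.08. On Reading 1 the ratio is exactly 1.00.

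| Reading | Rank of 4 | Separate terms | Combination that gives the interaction | The other combination |
|---|---|---|---|---|
| 1 Mirror image | 3 | not estimable | difference | identically zero |
| 2 Blocks, unconvolved | 3 | not estimable | difference | not estimable |
| 3 Blocks, convolved | 4 | VIF about 53 to 580 | difference | SD 1.96 |
| 4 Signed parts | 4 | VIF about 27 to 54 | sum | SD 1.19 |

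**The case against.** A reader might infer that the interaction cannot be estimated at all, that its standard error is some 24 times too large, or that Aim 3 is uninterpretable. The plan does not support any of these. Rank deficiency removes the separate coefficients, not the cue-versus-neutral contrast, which every reading recovers with little or no loss of precision. The 24-fold figure is √580; it applies to one separate term under one set of assumptions, not to the contrast.

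The defence has other fair points. The plan names the group-level target as cue against neutral, so a competent analyst would probably choose the combination that delivers it. Combining the two images therefore need not cancel the effect. The PPI approach cites method sources that may define the terms, and they were not available for this check. The VIFs depend on seed and response parameters that the plan does not give, so only a range is defensible. The imaging component is optional, and no sample size, power or alpha figure depends on this model.

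Two things still stand. The positive and negative terms might be loose wording for +1 and -1 contrasts on one regressor, but a one-term model has three regressors and the text counts four: "contrast images of the parameter estimates for each of the four regressors". And naming the target does not settle the weights, because the right combination is the difference on three readings and the sum on the fourth.

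**Conclusion.** The concern holds as a specification defect in the cue-based connectivity analysis. The two interaction terms are redundant on Readings 1 and 2 and strongly collinear on Readings 3 and 4, so the separate estimates that the plan promises are not identifiable or are imprecise. The interaction is recoverable, but the plan gives neither the combining weights nor the estimate that enters the 3A and 3B regressions. The wrong choice yields exactly zero on Reading 1 and an unstable estimate on Readings 3 and 4.

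The rank results and the zero sum follow from the plan's coding and block layout alone. The VIFs and SDs rest on the assumed seed series and response shape and should be read as orders of magnitude. The point should be corrected before the imaging analysis is run. It does not touch Hypotheses 1 and 2, nor Exploratory Hypothesis 4, which uses spectroscopy.

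**What to change.** For the alcohol and trauma runs, fit three regressors at first level: the signed task vector, the amygdala seed series and one signed task-by-seed product. Obtain the positive and negative effects as +1 and -1 contrasts on that one term. Carry only that contrast image to the group-level tests, and name it as the predictor in the cue-based 3A and 3B regressions.

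If two terms are kept for some reason, define how each is built, state the combining weights, and say which estimate goes into the regressions.

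The cost is a change to the first-level script and two sentences of text, with no new data. The change covers the cue runs only. No task vector is defined for the resting run, so what the interaction means there needs its own clarification.
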